Telemetry	X				X								Telemetry only required for doses > 200 mg and must start at least 60 min pre-dose and be continuous for 24h post-dose. See Section 8.2.5.
Holter monitoring	X				X		X		X				Holter monitoring must start at least 60 min pre-dose and be continuous for 24h post-dose.
12-lead ECG (Triplicate)	X	X	X		X		X		X	Q1W	X		On serial PK days (Day 1, 8 and 15), triplicate ECGs will be obtained at or about the time of each PK sample collection, as described in the SRM. On other days, triplicate ECGs will be obtained pre-dose.
Laboratory Assessments (Safety) – perform assessments pre-dose on each dosing day													
Clinical Chemistry, Urinalysis and Coagulations	X				X		X		X	Q1W	X		Refer to Appendix 2 for complete list of required laboratory assessments.
Hematology	X			X	X	X	X		X	Q1W	X		Hematology twice per week for the first two weeks (see Section 2.3.1). Refer to Appendix 2 for complete list of required laboratory assessments.
Pregnancy test					X				X	Q4W	X		Perform only in women of child bearing potential (WOCBP). Pregnancy tests during intervention phase and at discontinuation may be either serum

Procedure	DLT period (Days 1-21) ³								D22 ³	Continuation ³	TDV ¹	Follow-up	Notes		
	D1 ²	D2	D3	D4	D8	D11	D15	D16							
													or urine. Final pregnancy test must be performed within 150 days after last study intervention.		
Study intervention															
Administer study drug	X			←=====Daily Dosing=====→											A dose will be administered on Day 1, no dose will be given on Day 2 or Day 3 of the first cycle, after which, daily dosing will occur through the remainder of cycle 1 and all subsequent cycles. GSK3368715 should be administered in a fasted state at approximately the same time of day (\pm 4 h), with no food for 1 hour before and 2 hours after each dose. See Section 5.3.1 for dosing instructions on serial PK days.
Efficacy Assessment															
Tumor Imaging. Must include CT Chest. Must include CT abdomen if history of documented intraabdominal disease.										Week 9 Day1 then every 8 weeks until Week 33 Day 1 and then Q16W	X		Disease assessments will be performed until disease progression. Participants who discontinue for reasons other than PD will also be followed until the start of subsequent anti-cancer intervention. CR or PR should be confirmed as per response criteria in Appendix 10 .		
Patient Reported Outcomes															

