1. The assessments required at the treatment discontinuation visit (TDV) must be completed within 30 days from the date that study intervention was discontinued and must occur prior to the start of subsequent anti-cancer therapy; the window for this visit is +10 days

Table 4 Schedule of Activities (SoA) (Food effect cohort)

Food effect cohort (Section 4.1.1.1); samples collected in this section are in addition to any samples, studies, and visits described in Table 2) ³									
	D1	D2	D3	D4	D5 ⁴	D6	D7	D8	D9 and beyond
Administer study drug ¹	X				X				←-----daily dosing----->
Plasma PK samples ²	X	X	X	X	X	X	X	X	X ³

1. Study drug should be administered in fed or fasted state, based on assignment as described in Section 4.1.1.1
2. PK samples on Days 1 and 4/5 should be collected at 0 (pre-dose), 0.25h ± 5 min, 0.5h ± 5 min, 1h ± 5 min, 1.5h ± 5 min, 2h ± 10 min, 3h ± 10 min, 4h ± 10min, 6h ± 30 min, 8h ± 30 min, 12h ± 2h, 24± 2h, 48± 2h and 72± 2h hours post dose
3. Refer to Table 2 for subsequent PK sample requirements
4. In order to accommodate clinic schedules, the Day 5 dosing (including all PK assessments) may be performed one day earlier (on Day 4), i.e. Days 5 to 8 would shift to Days 4 to Day 7, and then all subsequent PK assessments from then on would follow the same schedule as in Table 2

NOTE: Participants in the food effect sub-study are subject to all screening, safety, PK, and efficacy evaluations detailed in Table 1 and Table 2. Samples collected in this section are in addition to any samples collected in Table 2, with the exception of Day 1-8 PK collections, in which the time points in Table 4 supersede those in Table 2

[figure not shown]
Any participant who experiences vomiting at or between 0.25-3 h will be removed from statistical analysis of PK comparability between fasted/fed state

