4.1.1.1. Food effect Cohort

Once a RP2D is identified, a food effect sub-study may be initiated. It will be an open-label, randomized, single dose, two period, cross over study to investigate the effect of a high-fat, high-calorie meal on the bioavailability of GSK3368715 with a tablet formulation at or near the RP2D. Initiation or completion of this sub-study is not required prior to initiating part 2. GSK3368715 dosing (fed then fasted, or fasted then fed) will be separated by at least 3days. A minimum of 12 participants in the United States may be enrolled in the sub-study. A participant requiring dose reduction or discontinuation from study before completion of at least 48 hours after dosing in fasted/fed state in the sub-cohort will be replaced by a new participant. All participants enrolled to the sub-study, on completion of their participation in this segment of the study, will continue on a daily dosing schedule until discontinuation criteria are met, as described in Section 7.1.

The food effect sub-study will be open to participants with histologically- or cytologically confirmed solid malignancies as described for Part 1 in Section 5.1.

The high-fat (approximately 50% of the total caloric content of the meal), high-calorie meal (approximately 800 to 1000 calories) will be the representative example given by the 2002 US Food and Drug Administration (FDA) guidance [FDA, 2002]. Additional details of the required meal will be provided in the SRM.

Participants enrolled in the sub-study will be assigned to one of two sequences, as described in [Table 5](#); equal numbers will be assigned to each sequence. The schedule of visits for participants enrolled in the sub-study is detailed in [Table 4](#) in Section 1.3. Upon completion of the sub-study, all participants will continue to undergo scheduled assessments as described in [Table 2](#). Additional details, including the process of sequence assignment, will be provided in the SRM.

Table 5 Food Effect Sub-Study

Food effect cohort (single dose administrations)			
Sample size	Sequence	Period 1 (W1D1)	Period 2 (W1D4/D5)
6	1	Fasted	Fed
6	2	Fed	Fasted

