4.3.2. Dose Justification for Food Effect Sub cohort

Food effect sub-study will be initiated at RP2D with tablets.

Preliminary physiologically based pharmacokinetic (PBPK) modeling suggests that GSK3368715 absorption is not limited by solubility or permeability, and is expected to be not as much affected by food. Further, PBPK modeling to-date and in vitro data from TinyTIM# suggest similar performance between capsules and tablets, and no substantial food effect.

#In-vitro model that mimics dynamic motility, volumes, secretion and digestion in the upper GI tract, designed by TNO/Triskelion [GlaxoSmithKline Document Number [2019N422334_01](#)]

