6.1. Study Intervention(s) Administered

The participants in each cohort will receive GSK3368715 orally, administered as either a capsule or tablet formulation (please refer to Section 1.2 and Section 1.3 for more detail).

During the DLT observation period, participants will only receive capsules, and may receive the tablet formulation if the participant continues on treatment at the end of Part 1.

Table 7 Study intervention

ARM Name	GSK3368715
Intervention Name	N/A
Type	Drug
Dose Formulation	
 1. API in Hydroxypropyl Methylcellulose (HPMC) Capsule 2. Immediate release (IR) white film-coated tablet containing API and excipients
Unit Dose Strength(s)	
 1. Capsule: 25 mg, 100 mg, 250 mg as free-base drug substance 2. Tablet: 50 mg, 100 mg and 250 mg as the free-base drug substance
Dosage Level(s)	As required by protocol
Route of Administration	Oral
IMP and NIMP	IMP (GSK3368715)
Sourcing	Provided centrally by the Sponsor
Packaging and Labelling	Study intervention will be labelled as required as per country requirement
Current/Former Name(s) or Alias(es)	N/A

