8.6. Pharmacokinetics

All participants enrolled in Part 1 (dose escalation/food effect) will receive a single dose on Day 1 and then begin continuous dosing after collection of the 72 hour PK sample. The timing of the PK samples may be altered and/or additional PK samples may be obtained at additional points to ensure thorough monitoring.

For details of PK sample collection, please refer to Section 1, [Table 2](#).

Day 1: participants will be administered GSK3368715 as a single oral dose followed by a 72 hour intervention-free period to evaluate PK. PK samples following Day 1 dose will be collected at Pre-dose, 15 ± 5 min, 30 ± 5 min, 1h ± 5 min, 1.5h ± 5 min, 2h ± 10 min, 3h ± 10 min, 4h ± 10 min, 6h ± 30 min, 8h ± 30 min, 12 ± 2h, 24 ± 2h, 48 ± 2h, 72 ± 2 hrs post-dose.

Day 8: PK samples will be collected at Pre-dose, 1.0h ± 5 min, and 4h ± 10 min post-dose.

Day 15: PK samples will be collected at Pre-dose, 30 ± 5 min, 1h ± 5 min, 2h ± 10 min, 3h ± 10 min, 4h ± 10 min, 6h ± 30 min, 8h ± 30 min, 12 ± 2h, and 24 ± 2h (prior to the next dose) post-dose.

PK samples on other visit days should be collected pre-dose only. All pre-dose PK samples at each visit should be collected within 1 hour prior to dose administration.

For details of PK sample collection for the PK/PD cohort in Part 1, please refer to Section 1.3, [Table 3](#).

For details of PK sample collection during the food effect cohort in Part 1, please refer to Section 1.3, [Table 4](#).

Meal times will be recorded on all PK collection days for Part 1 (dose escalation and PK/PD cohort) and on the dosing days (Days 1 and 5) in the food effect cohort.

Whole blood samples of approximately 2 mL will be collected for measurement of GSK3368715 and its metabolites as specified in the SoA. Blood may be collected at additional time points during the study if warranted and agreed upon between the investigator and the sponsor. Instructions for the collection and handling of biological samples will be provided by the sponsor. The actual date and time (24-hour clock time) of each sample will be recorded. Details of PK blood sample collection, processing, storage and shipping, procedures will be provided in study reference manual (SRM).

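### Protocol 8.6 and the food-effect sections give the food-effect cohort two incompatible dosing calendars, and no sentence says which governs

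*Protocol*

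**What the plan says.** **Dosing calendar.** Two sets of passages differ.

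- Protocol 8.6 opens with "All participants enrolled in Part 1 (dose escalation/food effect) will receive a single dose on Day 1 and then begin continuous dosing" after the 72-hour PK sample. Table 2 has the same pattern for Part 1 generally: "no dose will be given on Day 2 or Day 3 of the first cycle, after which, daily dosing will occur".
- Protocol 4.1.1.1 describes a "randomized, single dose, two period, cross over study" and states that "GSK3368715 dosing (fed then fasted, or fasted then fed) will be separated by at least 3days". Daily dosing follows only when the crossover segment is finished. Table 5 puts Period 2 on Day 4 or Day 5 of Week 1. Table 4 has its own drug-administration row: Day 1, Day 5, then daily from Day 9. It samples to 72 h after each single dose. Footnote 4 allows Period 2 a day earlier, so that "Days 5 to 8 would shift to Days 4 to Day 7".
- Further down, 8.6 itself says meal times are recorded "on the dosing days (Days 1 and 5) in the food effect cohort" and sends the reader to Table 4 for sampling.

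The note under Table 4 gives it precedence over Table 2 for PK collections on Days 1-8. It does not mention dosing.

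**Formulation.** Protocol 6.1: "During the DLT observation period, participants will only receive capsules". Protocol 4.3.2: "Food effect sub-study will be initiated at RP2D with tablets"; 4.1.1.1 also specifies a tablet. Section 6.1 writes no exception for the food-effect cohort and refers to 1.2 and 1.3 for detail.

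**Analysis.** Protocol 9.6.3.2.1 fits log Cmax and log AUC with fed status fixed and participant random. It has no period or sequence term. Absence of a food effect needs the 90% CI of the ratio to lie within 80-125%. SAP 2.1 states that the food-effect analysis will not be done.

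**The concern.** A single-dose crossover needs each period's profile to come from one dose. The opening of 8.6 names this cohort and starts daily dosing on Day 4, so Period 2 would not be a single-dose period:

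- If Period 2 is on Day 4, the doses on Days 5 and 6 fall inside its 72 h profile, and a third falls at the 72 h boundary.
- If Period 2 is on Day 5, a dose has also been given 24 h before it.

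AUC(0-t) would then mix the effect of food with accumulation. AUC(0-∞) and half-life would not be estimable from concentrations that rise between 24 h and 72 h. At stake is whether the sub-study could answer its own question. On formulation, the stake is which product the answer applies to.

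**Working it through.** **Inputs.** Terminal half-life 20-24 h (Protocol 2.2.1.5). N = 12, six per sequence (Table 5). CV 0.206, limits 0.80-1.25, true ratio 1.0, 10% level (9.2). Decision by 90% CI (9.6.3.2.1). Assumptions: one compartment, linear kinetics, peak near 1 h.

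**The plan's own figure.** For two one-sided tests on the log scale, σ_w = √ln(1 + 0.206²) = 0.204. With N = 12 and 10% per side, power is 80.1%, which reproduces the stated 80%. The 90% CI rule implies 5% per side. Power is then 60.6% on 10 df. With the stated model, which has no period term (11 df), it is about 62%. That 62% is the baseline below. The gap from 80% is a separate matter.

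**Carry-over.** Let r = 2^(−24/t½), so r = 0.435 at 20 h and 0.500 at 24 h. Taking absorption as fast:

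- Single-dose AUC(0-72) ∝ 1 − r³
- Added by a dose 24 h later: 1 − r²; by one 48 h later: 1 − r
- Residual from a dose j days earlier: r^j(1 − r³)

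At t½ = 24 h under 8.6:

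- Period 2 on Day 4: (0.875 + 0.750 + 0.500 + 0.125 × 0.875)/0.875 = 2.55
- Period 2 on Day 5: (0.875 + 0.750 + 0.500 + 0.0625 × 0.875 + 0.500 × 0.875)/0.875 = 2.99

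Period 2 relative to an isolated single dose, for half-lives of 20-24 h:

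| Calendar | Cmax, first 24 h | AUC(0-72) |
|---|---|---|
| Table 4, Day 5 | 1.04-1.06 | 1.04-1.06 |
| Table 4, Day 4 | 1.08-1.13 | 1.08-1.13 |
| 8.6, Period 2 on Day 4 | 1.08-1.13 | 2.55-2.58 |
| 8.6, Period 2 on Day 5 | 1.48-1.57 | 2.97-2.99 |

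These AUCs are true exposure. After 12 h, Table 4 samples only at 24, 48 and 72 h. If daily doses followed those samples, the later peaks would be missed, and the trapezoidal AUC(0-t) would be about 1.8 times (Day 4) or 2.2-2.3 times (Day 5).

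As a check on the model, it implies accumulation of 1/(1 − r) = 1.8 to 2.0. Protocol 2.2.1.5 reports mean Day 15 AUC up to 2-4 fold that of Day 1, so the assumption does not appear to exaggerate.

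**Effect on the decision.** Let L = ln(Period 2/Period 1). Each fed-minus-fasted difference is shifted by +L in one sequence and −L in the other.

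- *Point estimate.* With 6 v 6 the shifts cancel (simulated ratio 1.00). With 6 v 5 the estimate moves by L/11: 2.5^(1/11) = 1.09 and 3^(1/11) = 1.11, a 9-11% bias.
- *Spread.* With no period term, the SD of the differences is about √(2σ_w² + (12/11)L²). At L = 0 this is 0.288, and the 90% half-width is 1.796 × 0.288/√12 = 0.149, a typical interval of 0.86-1.16. At a ratio of 2.5, the SD is 1.00 and the half-width 0.518, giving 0.60-1.68. A centred interval needs a half-width below ln 1.25 = 0.223.

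Simulated chance of meeting the 80-125% rule with no true food effect:

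| Period 2/Period 1 ratio | Chance |
|---|---|
| 1.0 | 62% |
| 1.05 | 60% |
| 1.10 | 56% |
| 1.5 | about 3% |
| 2.0 and above | 0% |

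At 1.8, the low end of what sparse sampling would show, the chance is below 0.1%.

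**The case against.** The strongest reply is that every passage written for this sub-study agrees. Section 4.1.1.1, Table 5, Table 4's drug-administration row and the later sentence in 8.6 all describe two separate single doses. Section 5.3.1 also defers to 4.1.1.1 for the fed and fasted days. The harm arises only if a site follows one general sentence in a PK-sampling section against all of these. This stands: it is an inconsistency in the text, not a broken design. It does not remove the point, because the 8.6 sentence names the cohort and no passage states which dosing calendar takes precedence.

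Three stronger readings are tempting and are not supported.

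- *Capsules would invalidate the comparison.* They would not. Capsules in both periods still give a sound within-participant contrast, but for the capsule. The conflict is also less certain. The cohort opens only after an RP2D is identified, and 6.1 cites the schema, whose figure is not visible here. The amendment summary says that schema shows the capsule-to-tablet transition in this cohort. Against that, 1.1 and 4.1.1.1 place the cohort in Part 1, its participants follow Table 2 with Days 1-21 labelled as the DLT period, and 6.1 contains no exception.
- *Every PK measure is badly distorted.* With Period 2 on Day 4, Cmax is no worse than under Table 4 itself. The damage there is to AUC beyond 24 h.
- *The fed/fasted ratio is biased.* With balanced sequences it largely is not. The loss is in precision, and bias appears only as balance is lost.

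**Conclusion.** The dosing conflict is real and unresolved in the Amendment 3 text. If the opening of 8.6 were followed, Period 2 exposure would be about 2.5-3 times a single dose for AUC(0-72), or roughly 1.8-2.3 times as the planned samples would measure it. Either way the 80-125% criterion could not realistically be met for AUC(0-t), even with no food effect. The Cmax distortion is about 1.5 times for a Day 5 Period 2 and about 1.1 times for Day 4. These sizes rest on a one-compartment linear model, the stated half-life range, a CV of 0.206 and all sites following 8.6. The formulation conflict is secondary and held with less confidence.

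A reader might infer that a reported result is at risk. It is not: enrolment has stopped and SAP 2.1 drops the food-effect analysis. The point concerns the protocol text and any reuse of the sub-study design.

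**What to change.** Reconcile 8.6 and Table 2 with Table 4 and 4.1.1.1, so that a food-effect participant has one dosing calendar. Reconcile 6.1 with 4.1.1.1 and 4.3.2, so that the cohort has one stated formulation. Extend the precedence note under Table 4 to say which passage governs dosing as well as sampling for this cohort. No view is taken here on which dosing or formulation rule is right.

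An analysis rule that discards periods containing an extra dose would not replace this. It presupposes that Table 4 governs, and under 8.6 it would delete every Period 2.

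The cost is a few sentences, with no added visits, samples or participants. The SAP needs no change.

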8.7. Pharmacodynamics

8.7.1. Whole Blood

Whole blood samples will be collected for measurement of ADMA-hnRNP-A1 in peripheral blood mononuclear cells (PBMCs) and circulating free ADMA, SDMA and/or MMA levels in plasma as indicated in the SoA.

8.7.2. Tumor Biopsy

Tumor samples will be collected pre-dose and on-intervention from a limited number of participants for measurement of ADMA-hnRNP-A1, gene expression and immune markers such as, but not limited to, CD8 as indicated in the SoA (Section 1.3).

8.7.3. Tumor Biopsy Collection/Surgical Procedures

Biopsies collected during the study will only occur after participant consent and at dose levels deemed relevant in terms of safety and efficacy. Suitable participants will be identified by investigator and deemed acceptable by Medical Monitor. Fresh pre-treatment and on intervention biopsies are required for participants in PK/PD cohorts and optional for all other participants. During the study, it is expected that fresh biopsies will be provided pre-dose (within 14 days of the first dose), and at steady state (anticipated to be between Day 15 and Day 20) following GSK3368715 intervention. Additional optional timepoints include end of study and remission, especially if there is a question of residual viable tumor. No more than 4 fresh biopsies will be collected per participant as part of this study. Any fresh on-intervention biopsy should be accompanied by a plasma sample for PK analysis collected as close as possible to the time of biopsy (preferably within 1 h)

Participants undergoing fresh biopsies must have a platelet count of $\geq 75,000/\text{mm}^3$ and a PT, international normalized ratio (INR) and aPTT that are within normal limits and taken within 48 hours prior to the post-dose biopsy or any other planned surgical procedure. Further details regarding sample type and processing will be provided in the SRM.

8.8. Genetics

Information regarding genetic research is included in [Appendix 5](#).

A 6 mL blood sample for DNA isolation will be collected from participants who have consented to participate in the genetics analysis component of the study. Participation is optional. Participants who do not wish to participate in the genetic research may still participate in the study.

In the event of DNA extraction failure, a replacement genetic blood sample may be requested from the participant. Signed informed consent will be required to obtain a replacement sample unless it was included in the original consent.

Details on processes for collection and shipment and destruction of these samples can be found in SRM.

8.9. Biomarkers and Translational Research

8.9.1. Samples

After completion of the clinical trial and/or during the conduct of the study, investigations may be performed on samples collected during the trial to detect factors or profiles that correlate with response to intervention with GSK3368715. Performance of these investigations may be conditional on the results of the clinical trial and samples will be selected for analysis on the basis of the clinical outcome.

Samples may be tested for immunophenotyping to evaluate the association with efficacy in response to intervention with GSK3368715. Additionally, comparative examination of post-dosing profiles in conjunction with pre-dosing profiles may yield known and novel candidate biomarkers/profiles and new insights which relate to the action of GSK3368715.

All samples will be retained for the length of time described in participant ICFs after the last participant completes the trial.

Novel candidate biomarkers and subsequently discovered biomarkers of biological response associated with lymphoma and solid tumors and/or the action of GSK3368715 may be identified by application of:

- DNA, RNA and protein analysis of tumor tissue.
- DNA, RNA and protein analysis of PBMCs.
- Circulating protein analysis of plasma.
- Immunophenotyping of PBMCs and/or tumor tissues.
- Coagulation markers from plasma and serum samples

Blood samples will be collected according to the SoA (Section 1.3). One or more timepoints could be removed with emerging data.

8.9.2. Exploratory Tumor Biomarker Analysis

To further characterize the participant population, DNA, RNA and/or protein measurements may be utilized to identify predictors of sensitivity or resistance to GSK3368715 utilizing baseline tissue (archival tissue or a recent biopsy) and in tissue obtained at disease progression.

8.9.3. Circulating Protein Analysis

Blood-based markers have the important advantage that specimens are readily available, simple to prepare and store, and can be obtained prior to and during intervention. This allows for the assessment of predictive markers based on the baseline evaluation as well as markers of activity and resistance based on changes that occur during and/or after intervention. Additionally, levels of protein in plasma samples may be analyzed to better understand modulation of secretory proteins from the tumor or the immune system in response to intervention with GSK3368715 and how this correlates with efficacy. For instance, plasma samples collected at the time points provided in the SoA may be analyzed for Interferon gamma (IFN-gamma) and Tumor Necrosis Factor (TNF-alpha) signatures by investigating a panel of pro-inflammatory cytokines, immuno-regulatory factors and chemokines.

